This study was approved by the Beaumont Institutional Review Board (2019-224). Patients who presented to Beaumont Royal Oak and Beaumont Troy for a routine inguinal hernia repair (ages 2-13 years) or laparoscopic appendectomy for uncomplicated appendicitis (ages 0-17 years) were eligible for participation. Patients meeting eligibility criteria (**Figure 1**) were identified by the pediatric surgeons, including the Primary Investigator ([name]), and were provided with an information sheet detailing the study, which served as consent for participation. Parents and patients who elected to participate then chose to enroll in the control group (PDAR) or experimental group (SDAR). The PDAR instructions detailed that patients are restricted from full, normal activity for 2 weeks after their procedure. The SDAR instructions specified that they may return to full activity when their pain is improving and the parent, or guardian, feels comfortable advancing their activity. Enrollment is still accruing for this study.

Figure 1. Patient eligibility criteria**Figure 1.** Patient eligibility criteria for participation in the clinical trial.

Data Collection

Baseline characteristics, comorbidities, surgical complications, length of stay, and pain medications will be obtained for each participant from the time of surgery. At 4-6 weeks postoperatively, parents or guardians will be asked to complete a survey at their follow-up appointment or online using Research Electronic Data Capture (REDCap). The survey includes assessments of the time taken to return to school and work, return to full activity, surgical complications, and patient and caregiver satisfaction (**Figure 2**).

Figure 2. Postoperative Survey

Your Child's Experience Postoperatively	
For how long was your child on pain medications following the procedure?	 1-2 days  3-4 days  4-7 days  >1 week
How many days following the procedure did your child return to school, daycare, summer camp, or summer school?	
Approximately how many days after surgery did your child return to full activity (sports, gym, dance, outdoor play, etc.)?	
Did your child's wound have any oozing or bleeding following discharge from the hospital?	 None  Mild (slight drainage)  Moderate (drainage with blood)  Severe (oozing with blood)

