If you answered mild, moderate, or severe to the previous question, when did this occur?	
If you answered mild, moderate or severe to the previous question, did this require any treatment by your surgical team?	
Did your child experience any postoperative complications?	 No  Yes
If you answered yes to the previous question, please specify:	
After resuming full activity, did your child experience an increase in pain?	 No  Yes
If you answered yes to the previous question, did they require any medication for the pain?	 No  Yes
How compliant was your child with their postoperative instructions?	 Compliant  Partially compliant  Not compliant

Postoperative Activity Restrictions in Children After Routine Surgery

5

How would you describe your child's overall satisfaction following the procedure?	 Very satisfied  Satisfied  Neither satisfied or dissatisfied  Dissatisfied  Very dissatisfied
Your Experience Postoperatively	
What is your relationship to the child?	 Mother  Father  Grandparent  Legal Guardian  Other
Did you or another caregiver take time off work to care for your child following their procedure?	 Yes  No
Did you have to find additional childcare for your child following their procedure?	 Yes  No
How would you describe your overall satisfaction following your child's procedure?	 Very satisfied  Satisfied  Neither satisfied or dissatisfied  Dissatisfied  Very dissatisfied
Were you satisfied with the instructions detailed in your discharge guidelines?	 Very satisfied  Satisfied  Neither satisfied or dissatisfied  Dissatisfied  Very dissatisfied

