If your followed physician-directed instructions, did you follow the recommendations strictly?	 Yes  No  Somewhat
If you chose self-directed instructions, did you feel comfortable determining when your child was able to resume full activity?	 I felt comfortable  I had some concerns  I did not feel comfortable

Figure 2. Postoperative survey provided to patients 4-6 weeks following their procedure. Patients were able to complete the survey at their postoperative visit or online via REDCap.
	

Objectives

The primary outcome of this study is length of time to full activity.

Secondary outcomes will evaluate patient preference to PDAR and SDAR based on choice of study arm and the impact of restriction type on number of parental days off work.

Clinical complications will also be tracked. Patient satisfaction will be defined as a cumulative score of three satisfaction factors (child, parent, and satisfaction with discharge guidelines).

Statistical Analysis

Continuous data will be presented as mean (SD) or median (IQR) depending on distribution, and analyzed using unpaired t tests or Mann Whitney ranked sum tests. Categorical data will be presented as number (%) and will be analyzed using Chi Square or Fisher's exact test depending on frequencies P values <.05 will be considered significant.

REFERENCES

3. Pommergaard H-C, Burcharth J, Danielsen A, Angenete E, Haglind E, Rosenberg J. No consensus on restrictions on physical activity to prevent incisional hernias after surgery. *Hernia*. 2014;18(4):495-500. doi:10.1007/s10029-013-1113-8

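### The plan names no test that uses order, so the ordered survey items fall by default to Chi-square or Fisher's exact test, which ignore it (minor)

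*Combined protocol and SAP*

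**What the plan says.** The Statistical Analysis section has two rules. Continuous data are to be "analyzed using unpaired t tests or Mann Whitney ranked sum tests". For the rest: "Categorical data will be presented as number (%) and will be analyzed using Chi Square" or Fisher's exact test, the choice resting on the frequencies. The threshold is "P values <.05 will be considered significant". Ordinal data are not mentioned, and no survey item is assigned to either rule.

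The postoperative survey (Figure 2) contains several ordered tick-box items:

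- the question whether the child's "wound have any oozing or bleeding following discharge from the hospital", with four grades from none to severe;
- duration of pain medication, in four bands;
- compliance with instructions, at three levels;
- three five-level satisfaction items, one of which asks "Were you satisfied with the instructions detailed in your discharge guidelines".

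Under Objectives, the primary outcome is time to full activity, and the outcomes labelled secondary are choice of arm and parental days off work. Two further statements concern the ordered items: "Clinical complications will also be tracked", and "Patient satisfaction will be defined as a cumulative score of three satisfaction factors (child, parent, and satisfaction with discharge guidelines").

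**The concern.** Chi-square and Fisher's exact test treat the levels as unordered labels. Exchanging mild and severe oozing throughout the data would leave the P value unchanged. When one arm is shifted steadily towards worse grades, a test with k − 1 degrees of freedom spreads its sensitivity over patterns that are not of interest, while a rank or trend test puts it on the shift.

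This matters most for wound oozing. The Background section says that restrictions are meant to limit complications and protect the operative site, so a comparison of self-directed with physician-directed restrictions has a safety side. Oozing is the only complication item in the survey with severity grades; the general complication question is yes/no. A shift towards more oozing in one arm would be less likely to be detected than the data allow.

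**Working it through.** **No figure to reproduce.** The documents state no sample size, power, effect size or category shares. The number of levels (3, 4, 5) and the 0.05 threshold come from the documents. Everything else below is assumed, including a two-sided test.

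**Step 1: analytic check, free of assumed shares.** Suppose that a 1-df ordered test has 80% power. Its noncentrality is

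λ = (1.960 + 0.842)² = 7.85.

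If the difference lies wholly in the ordered direction, Chi-square has the same λ but k − 1 degrees of freedom, so its power is P(χ²(k − 1, λ) > critical value).

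| Levels k | df | Critical value | Chi-square power | Loss against 80% |
|---|---|---|---|---|
| 3 | 2 | 5.99 | 70.9% | 9 points |
| 4 | 3 | 7.81 | 64.5% | 15–16 points |
| 5 | 4 | 9.49 | 59.5% | 20–21 points |

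**Step 2: simulation.** Pearson Chi-square was compared with the tie-corrected Mann-Whitney test under proportional-odds shifts tuned to about 80% Mann-Whitney power. Arms were 50:50, 100:100 and 60:140; the last is included because families choose their arm.

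| Item | Assumed baseline shares (%) | Chi-square power | Loss |
|---|---|---|---|
| Compliance | 70/22/8 | 70.1–70.8% | 9–10 points |
| Pain-medication duration | 35/35/20/10 | 63.3–64.1% | about 16 points |
| Oozing | 80/14/4/2 or 90/7/2/1 | 54.5–63.5% | 16–26 points |
| Single satisfaction item | 55/30/10/3/2 or 20 at each level | 54.5–61.2% | 19–26 points |

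With the odds ratio set at 1.5, 2 or 3 instead, the loss ran from about 3 to 28 points. It was smallest where both tests had high power, and largest for sparse oozing at 60:140. Part of the loss with sparse oozing arises because Chi-square is then conservative: under no difference at 50 per arm it rejected in 2.5–2.8% of trials, against about 5% for Mann-Whitney. Fisher's exact test was not simulated.

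**Step 3: one oozing example in detail.** Assumed shares are 80/13/5/2% against 65/22/9/4%, with 100 per arm.

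- Four-level Chi-square 49%, Mann-Whitney 66%.
- Moderate and severe merged: Chi-square 56%, Mann-Whitney 66%.
- Any against none, by Chi-square: 66%.
- Under no difference (80/13/5/2% in both arms): Chi-square 4.3%, Mann-Whitney 5.1%.

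**Step 4: where the ranking reverses.** If the share with any oozing stays at 80/20 and only severity changes (80/18/1.5/0.5% against 80/8/8/4%, assumed, 100 per arm), Chi-square has about 82% power and Mann-Whitney 6%. A five-level example without a consistent direction (55/30/10/3/2% against 45/50/3/1/1%) gave 77% and 9%.

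**Step 5: the satisfaction score.** If each item is scored 1 to 5 (the scoring is not stated), the sum of three runs from 3 to 15, which is 15 − 3 + 1 = 13 values. Such a score fits the t test or Mann-Whitney rule at least as well as the categorical rule.

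**The case against.** The case on the other side has real weight.

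- **The plan does not assign these items to Chi-square.** True; that is an inference from the categorical rule. It is the natural reading for tick-box items, and if the sponsor means otherwise the plan needs to say so.
- **Satisfaction.** A reader might infer that the satisfaction outcome itself is to be tested without regard to order. The documents do not support that: it is defined as a summed score, and nothing says that its three items will be tested singly. What remains is that no test is named for the score.
- **Any-against-none oozing already fits the plan and loses nothing.** In the Step 3 example this is correct. But the plan does not specify that split, and the split cannot detect a change in severity alone.
- **A rank test can hide a severity-only change.** Step 4 confirms it, so the change is cheap but not free. The order of the top two oozing grades is also not clear-cut, since both descriptions involve blood.
- **Chi-square is valid.** It holds its error rate at or below 5%; the issue is efficiency.
- **Compliance means different things in the two arms**, a two-week restriction in one and self-direction in the other. No choice of test makes that comparison informative.

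**Conclusion.** The point holds as a minor one. The plan names no method that uses order, and its categorical rule would discard the order of oozing, pain-medication duration, compliance and any satisfaction item compared singly. Against an ordered test with 80% power, Chi-square has about 71%, 64% and 60% with 3, 4 and 5 levels. Those figures assume a shift in one direction.

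Two stronger readings are tempting. One is that the plan costs a fixed 15 to 20 points of power. That range fits four- and five-level items near 80% power, but three-level compliance loses only 9 to 10, and without a sample size, effect size or category shares the loss in this trial cannot be known. The other is that a safety signal will be missed and the result taken as reassurance. The documents say only that complications are tracked; they do not say that oozing will be formally compared or how a non-significant result will be read. They also provide a yes/no complication item, a question on treatment for oozing, and complication data obtained from the time of surgery. None of the affected items is a primary or labelled secondary outcome.

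**What to change.** Add to the Statistical Analysis section:

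> Ordered categorical items (wound oozing, pain-medication duration, compliance, and any satisfaction item analysed singly) will be compared with the tie-corrected Mann-Whitney test or a proportional-odds model (common odds ratio, 95% CI). The cumulative satisfaction score will be compared with the Mann-Whitney test. Chi-square or Fisher's exact test will be used for unordered or two-level items.

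Keep the number and percentage at each level in the tables, so that a change in severity without a change in the share with any oozing stays visible. One of the two methods should be chosen before the data are analysed.

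The cost is small: Mann-Whitney is already in the plan and no data collection changes. The downside is lower sensitivity when the arms differ without a consistent direction, which the level-by-level table guards against only descriptively.
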